#### Incomplete assessment dates for tumor assessment

All investigation dates (e.g. MRI scan, CT scan) must be completed with day, month and year. If one or more assessment dates are incomplete but other investigation dates are available, this/these incomplete date(s) are not considered for calculation of the assessment date and assessment date is calculated as the latest of all investigation dates (e.g. MRI scan, CT scan) if the overall response at that assessment is CR/PR/SD/UNK. Otherwise – if overall response is progression – the assessment date is calculated as the earliest date of all investigation dates at that evaluation number. If all measurement dates have no day recorded, the 1st of the month is used. If the month is not completed, for any of the investigations, the respective assessment will be considered to be at the date which is exactly between previous and following assessment. If a previous and following assessment is not available, this assessment will not be used for any calculation.

## Applying the cut-off to tumor assessment

For tumor related assessments, if an evaluation has some assessments done prior to cut-off date and others after the cut-off date, then the evaluation is considered post-cut-off date and will be excluded from analysis.

Novartis	Confidential	Page 41
SAP	22-Feb-2022 (1:27)	CLEE011A2404

## 5.2 AEs coding/grading

Adverse events are coded using the Medical dictionary for regulatory activities (MedDRA) terminology.

AEs will be assessed according to the Common Terminology Criteria for Adverse Events (CTCAE) version 4.03.

The CTCAE represents a comprehensive grading system for reporting the acute and late effects of cancer treatments. CTCAE grading is by definition a 5-point scale generally corresponding to mild, moderate, severe, life threatening, and death. This grading system inherently places a value on the importance of an event, although there is not necessarily proportionality among grades (a grade 2 is not necessarily twice as bad as a grade 1).

## 5.3 Laboratory parameters derivations

Grade categorization of lab values will be assigned programmatically as per NCI Common Terminology Criteria for Adverse Events (CTCAE) version 4.03. The calculation of CTCAE grades will be based on the observed laboratory values only, clinical assessments will not be taken into account. The criteria to assign CTCAE grades are given in Novartis internal criteria for CTCAE grading of laboratory parameters. The latest available version of the document based on the underlying CTCAE version 4.03 at the time of analysis will be used. For laboratory tests where grades are not defined by CTCAE v4.03, results will be graded by the low/normal/high (or other project-specific ranges, if more suitable) classifications based on laboratory normal ranges.

A severity grade of 0 will be assigned for all non-missing lab values not graded as 1 or higher. Grade 5 will not be used. For laboratory tests that are graded for both low and high values, summaries will be done separately and labelled by direction, e.g., sodium will be summarized as hyponatremia and hypernatremia.

## Multiple lab assessments

Specific rules for defining the baseline when there are multiple lab measurements taken at the last assessment date on or before the start date of study treatment are presented below:

As a general rule the lab value among the multiple measurements with the lowest CTCAE grade will be considered as the baseline value.

## Imputation Rules

CTC grading for blood differentials is based on absolute values. However, this data may not be reported as absolute counts but rather as percentage of White Blood Cell (WBC).

If laboratory values are provided as '<X' (i.e. below limit of detection) or '>X', prior to conversion of laboratory values to SI unit, these numeric values are set to X.

The following rules will be applied to derive the WBC differential counts when only percentages are available for a xxx differential:

```
xxx count = (WBC count) * (xxx %value / 100)
```

Novartis	Confidential	Page 42
SAP	22-Feb-2022 (1:27)	CLEE011A2404

Further derivation of laboratory parameters might be required for CTCAE grading. For instance, corrected calcium can be derived using the reported total calcium value and albumin at the same assessment using the following formula:

Corrected Calcium (mg/dL) = Calcium (mg/dL) - 0.8 [Albumin (g/dL)-4]

In order to apply the above formula, albumin values in g/L will be converted to g/dL by multiplying by 0.1), calcium values in mmol/L will be converted to mg/dL by dividing by 0.2495. For calculation of laboratory CTC grades 0 and 1, the normal range for derived corrected calcium is set to the same limits (in mg/dL) as for calcium.

CTC grades for the derived absolute WBC differential counts (neutrophils, lymphocytes) and corrected calcium will be assigned as described above for grading.

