Toxicity/Grade	Dose Adjustment and Management Recommendations
Thrombocytopenia	
Grade 1(≥75 x 10 ⁹ /L)	No dose adjustment required.
Grade 2 (≥50 x 10 ⁹ /L – <75 x 10 ⁹ /L)	Dose interruption until recovery to grade ≤1. Re-initiate ribociclib at the same dose.
Grade 3 (≥25 x 10 ⁹ /L - <50 x 10 ⁹ /L)	Dose interruption until recovery to grade ≤1. Re-initiate ribociclib at the same dose level. If toxicity recurs at grade 3: temporary dose interruption until recovery to grade ≤1 and reduce ribociclib to the next lower dose level.
Grade 4(<25 x 10 ⁹ /L)	Dose interruption until recovery to grade ≤1. Re-initiate ribociclib at the next lower dose level. If toxicity recurs at grade 4: discontinue ribociclib
Absolute neutrophil count (ANC)	
Grade 1 (≥1.5 x 10 ⁹ /L)	No dose adjustment required.
Grade 2 (≥1.0 - <1.5 x 10 ⁹ /L)	No dose adjustment required.
Grade 3 (≥0.5 - <1.0 x 10 ⁹ /L)	Dose interruption until recovery to $\geq 1.0 \times 10^{9}$ /L. Re-initiate ribociclib at the same dose level. If toxicity recurs at grade 3: temporary dose interruption until recovery to $\geq 1.0 \times 10^{9}$ /L. If resolved in ≤ 7 days, then maintain dose level. If resolved in ≥ 7 days, then reduce ribociclib dose to the next lower dose level.
Grade 4 (<0.5 x 10 ⁹ /L)	Dose interruption until recovery to $\ge 1.0 \times 10^{9}$ /L. Re-initiate ribociclib at the next lower dose level.

Table 6-3Ribociclib dose reduction/interruption and management
recommendations for hematological adverse drug reactions (CTCAE
v4.03)

Toxicity/Grade	Dose Adjustment and Management Recommendations
Febrile neutropenia	
Grade 3 ANC <1.0 x 10^{9} /L with a single temperature of >38.3 °C (101 °F) or a sustained temperature of ≥38 °C (100.4 °F) for more than one hour	Dose interruption until improvement of ANC $\ge 1.0 \times 10^9$ /L and no fever. Restart at the next lower dose level. If febrile neutropenia recurs, discontinue ribociclib.
Grade 4 Life-threatening consequences; urgent intervention indicated	Discontinue ribociclib.
Anemia (Hemoglobin)	
Grade 1 (≥10.0 – LLN g/dL)	No dose adjustment required.
Grade 2 (≥8.0 – <10.0 g/dL)	No dose adjustment required.
Grade 3 (<8.0 g/dL)	Dose interruption until recovery to grade \leq 2. Re-initiate ribociclib at the same dose.
Grade 4 Life-threatening consequences; urgent intervention indicated	Discontinue ribociclib.

Table 6-4Ribociclib dose reduction/interruption and management
recommendation for hepatic toxicities (CTCAE v4.03)

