Increase from baseline grade 0 or 1 to grade 3 (> 5.0 – 20.0 x ULN)	Dose interruption of ribociclib until resolved to ≤ baseline grade, then lower 1 dose level of ribociclib Repeat liver enzyme and bilirubin tests twice weekly for 2 weeks after dose resumption If recovery to ≤ baseline grade is > 28 days, discontinue ribociclib	
Increase from baseline grade 2 to grade 3 (> 5.0 – 20.0 x ULN)	Dose interruption of ribociclib until resolved to ≤ baseline grade, then lower 1 dose level of ribociclib Repeat liver enzyme and bilirubin tests twice weekly for 2 weeks after dose resumption If toxicity recurs after two dose reductions or recovery to ≤ baseline grade is > 28 days, discontinue ribociclib.	
Grade 4 (> 20.0 x ULN)	Discontinue ribociclib	
AST or ALT and concurrent Bilirubin		
For patients with normal ALT and AST and total bilirubin at baseline: AST or ALT >3.0 x ULN combined with total bilirubin > 2 x ULN without evidence of cholestasis Or For patient with elevated AST or ALT or total bilirubin at baseline: baseline: [AST or ALT >2 x baseline AND >3.0x ULN] OR [AST or ALT 8.0 x ULN]- whichever is lower- combined with [total bilirubin > 2 x baseline AND >2.0 x ULN]	Discontinue ribociclib	
Confounding factors and/or alternative causes for interruption/reduction. They include but are not li dietary supplements, infection, hepato-biliary dis	I or increased transaminases should be excluded before dose mited to: concomitant medications, herbal preparations or order or obstruction, new or progressive liver metastasis, and	

dietary supplem alcohol intake.

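### Setting `<X` and `>X` laboratory results equal to X before CTCAE grading under-grades any low count or high liver test censored exactly at a grade limit

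*SAP*

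**What the plan says.** The imputation rules in SAP 5.3 cover results that arrive with an inequality sign: "If laboratory values are provided as '<X' (i.e. below limit of detection) or '>X"', in which case, "prior to conversion of laboratory values to SI unit, these numeric values are set to X". The lower form is explained as a detection limit; the upper form carries no explanation.

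Grading then works on the number. SAP 5.3 says "Grade categorization of lab values will be assigned programmatically as per NCI Common Terminology Criteria for Adverse Events (CTCAE) version 4.03" and "The calculation of CTCAE grades will be based on the observed laboratory values only, clinical assessments will not be taken into account". It also says where the programmed limits are held: "The criteria to assign CTCAE grades are given in Novartis internal criteria for CTCAE grading of laboratory parameters". That internal document is not reproduced.

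The limits that can be seen are in Protocol 6.3.1.3, in tables headed CTCAE v4.03. For ANC (unit 10^9/L), Table 6-3 has "Grade 3 (≥0.5 - <1.0 x 10" and then "Grade 4 (<0.5 x 10". For AST/ALT, the top row of Table 6-4 is "Grade 4 (> 20.0 x ULN". Platelets, hemoglobin and total bilirubin follow the same pattern: the limit itself belongs to the milder grade.

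**The concern.** A result of ANC `<0.5` tells us that the count is below 0.5. Replacing it by 0.5 discards the one fact that decides the grade and places the value at the mildest edge of Grade 3. For low counts and high liver tests the error can run only one way, toward milder toxicity.

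The outputs at stake are the programmed laboratory summaries in SAP 2.8.4: worst post-baseline grade, shift tables, grade labels in the listings, and the liver-threshold counts. All laboratory work is done locally (Protocol 7.2.2.5) and pooled, so reporting limits may differ between laboratories. These tables are also the one view of laboratory toxicity that does not depend on what investigators chose to report as an adverse event.

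**Working it through.** The plan states no figure that depends on this rule, so there is none to reproduce. The check applies the SAP rule (value := X) to each numeric limit in Protocol Tables 6-3 and 6-4 and compares the resulting grade with the grades of all values that the report allows. ANC and platelets are in 10^9/L, hemoglobin in g/dL, and liver tests in multiples of ULN.

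| Reported result | Value used | Grade under the SAP rule | Grade(s) the report allows |
|---|---|---|---|
| ANC `<0.5` | 0.5 | 3 | 4 |
| ANC `<1.0` | 1.0 | 2 | 3 or 4 |
| ANC `<1.5` | 1.5 | 1 | 2 to 4 |
| Platelets `<25` | 25 | 3 | 4 |
| Platelets `<50` | 50 | 2 | 3 or 4 |
| Platelets `<75` | 75 | 1 | 2 to 4 |
| Hemoglobin `<8.0` | 8.0 | 2 | 3 (numeric limits only) |
| Hemoglobin `<10.0` | 10.0 | 1 | 2 or 3 |
| Bilirubin `>10` | 10 | 3 | 4 |
| Bilirubin `>3` | 3 | 2 | 3 or 4 |
| Bilirubin `>1.5` | 1.5 | 1 | 2 to 4 |
| ALT/AST `>20` | 20 | 3 | 4 |
| ALT/AST `>5` | 5 | 2 | 3 or 4 |
| ALT/AST `>3` | 3 | 1 | 2 to 4 |

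All 14 limits come out at least one grade too mild. The shortfall is exactly one grade at the Grade 4 limits and at hemoglobin 8.0; elsewhere it can be larger. Unit conversion does not help: `<500/µL` becomes 0.5 and Grade 3.

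When X is not on a limit:
- ANC `<0.1`, `<0.2`, `<0.3`, `<0.4` and `<0.49` are all graded 4, which is right.
- ANC `<0.6` is graded 3, while the truth may be Grade 3 or 4. This is a possible error, not a certain one.

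Derived counts: SAP 5.3 computes a differential count as WBC × percentage / 100 when only the percentage is available. With WBC `<1.0` and 50% neutrophils (an illustration), the rule gives 1.0 × 50/100 = 0.5, Grade 3. The true ANC is below 0.5, Grade 4. On this route the reported limit need not itself be a grade limit.

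Effect on each output:
- Worst-grade and shift tables: the patient moves to a milder category if that result determines the worst grade.
- Grade 3/4 listing: a Grade 4 result graded 3 stays in the listing with the wrong label. A record drops out only at the Grade 2/3 limit, as with ANC `<1.0`.
- Liver thresholds: ALT set to 20 × ULN still satisfies >3, >5, >8 and >10. Only >20 is missed.

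**The case against.** The strongest reply is that the rule was written for detection limits. The SAP says so for `<X`, and a detection limit deep inside Grade 4 is graded correctly. Nothing in the documents shows that any laboratory reports ANC as `<0.5` or platelets as `<25`, and an ALT ceiling of exactly 20 times a laboratory's own ULN would be a coincidence. This stands as an argument about frequency. It does not remove the error: the rule as written applies to every `<X` result, the explanation does not extend to `>X`, and no other section keeps the sign.

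A reader might infer that the primary endpoint or the AESI results understate severe neutropenia and liver toxicity. The documents do not support that. The primary endpoint counts patients with reported adverse events (SAP 2.5.1), AE severity is graded as part of AE reporting (Protocol 8.1.1) and summarized at the maximum recorded grade (SAP 2.8.1), and AESIs are MedDRA groupings of reported events (SAP 2.8.2). None uses the programmed laboratory grade. Laboratory abnormalities that require a change in study treatment must also be reported as AEs (Protocol 8.1.2.1), so severe events have a separate route into the AE tables.

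A reader might also infer that the Grade 3/4 listing loses Grade 4 events, or that only results exactly on a limit are at risk. Neither is right, as the working shows. Nor can a patient count be put on the effect: it would need the rate of Grade 4 results and the share of them seen only as a censored value, and the documents give neither share.

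**Conclusion.** The point holds as a narrow defect in the programmed laboratory summaries. A result censored exactly at a grade limit is certain to be graded at least one grade too mild; one whose possible values span a limit may be; one whose limit lies inside Grade 4 is not. The primary AE endpoint and the AESI summaries are untouched. The number of patients affected cannot be computed from the documents and may be small or zero.

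This rests on two assumptions: that the internal grading criteria use the same CTCAE v4.03 limits as the protocol tables, and that they contain no separate provision for censored values. It is still worth correcting, because a stated rule gives a grade known to be wrong in planned safety tables and the remedy costs very little.

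**What to change.** In the imputation rules of SAP 5.3, restrict the use of X to continuous summaries and box plots. For CTCAE grading and for the liver-threshold counts, retain the sign: treat `<X` as strictly below X and `>X` as strictly above X when comparing with a limit, including when ANC is derived from a censored WBC. Comparing by sign is preferable to subtracting one reporting unit, which would need each laboratory's reporting precision.

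Under this rule ANC `<0.5` becomes Grade 4 and `<1.0` at least Grade 3. ANC `<0.6` stays at Grade 3 because Grade 4 is not certain. The number of censored results at or spanning a grade limit should therefore be reported by parameter, so that the reader can see what uncertainty remains; if the count is zero, the matter is closed.

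The cost is a sentence in the SAP and a small change to the grading and threshold programs. No new data are needed, since the existing rule already works from results that carry the sign.

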## 5.4 Statistical models

#### Analysis of time to events Data

#### Kaplan-Meier estimates

An estimate of the survival function will be constructed using Kaplan-Meier (product-limit) method as implemented in PROC LIFETEST with METHOD=KM option. The PROC LIFETEST statement will use the option CONFTYPE=LOGLOG.

Median survival for each treatment group will be obtained along with 95% confidence intervals calculated from PROC LIFETEST output using the method of (Brookmeyer and Crowley 1982). Kaplan-Meier estimates of the survival function with 95% confidence intervals at specific time points will be summarized. The standard error of the Kaplan-Meier estimate will be calculated using Greenwood's formula (Collett 1994).

#### Analysis of Binary Data

#### Confidence interval for response rate

Responses will be summarized in terms of percentage rates with  $100(1 - \alpha)\%$  confidence interval using exact binomial confidence interval (implemented using SAS procedure FREQ with EXACT statement for one-way table (Clopper and Pearson 1934).

